3.6. Subject Replacement

Participants withdrawn will be replaced.

4. TRIAL SCHEDULE

Week	Blood	Treatment Leg 1	Treatment Leg 2	Activity and Diet Questionnaire
1	✓	✓	✓	✓
2		✓	✓	
3		✓	✓	
4		✓	✓	
5	✓			✓
6				
7				
8	✓			✓

Figure 1: The breakdown of the events that will be happening on each week. Blood will be collected on Week 1, 5 and 8 with a set of questions found in the questionnaire will be assessed on Week 1, 5 and 8.

Early Week (Mon/Tue) recruitment					
Mon	Tue	Wed	Thu	Fri	Sat
Leg 1	Leg 1		Leg 2	Leg 2	
Visit 1			Visit 2		

Late Week (Thu/Fri) recruitment					
Thu	Fri	Sat	Sun	Mon	Tue
Leg 1	Leg 1			Leg 2	Leg 2
Visit 1				Visit 2	

Figure 2: The PEMF treatment schedule depending on the recruitment days as a minimum of two days gap is required in between each treatment with alternate legs.

5. STUDY DESIGN

The study is designed as a double-blinded, randomised, controlled pilot study. Recruitment will be in groups of 10 study participants. In each group of 10, participants will randomized to either sham or treatment group based on the RFID card that they will be assign to. Subject randomisation ID will coincide with RFID card number. Each participant will use the assigned RFID card to tap onto the RFID reader in order to activate the PEMF leg coil. Randomization and blinding is assigned by QuantumTX, the company that develops the PEMF leg coil device together with the RFID system.

5.1. Summary of Study Design

Participant will receive either PEMF or no PEMF twice in a week for 4 consecutive weeks. In each week, the participant will place their upper thigh into the PEMF leg coil to receive the treatment. A minimum of two days of rest is required before the next treatment is administered. The participant will also alternate their legs for every treatment session.

6. METHODS AND ASSESSMENTS

Blood sample collection

Blood from study participants will be collected at Week 1 (before the start of the PEMF treatment as a baseline), Week 5 (one week after completion of 8 sessions of PEMF treatment) and Week 8 (4 weeks after completion of 8 sessions of PEMF treatment). Blood will be collected in EDTA tubes and processed for multiplex and ELISA to assess the blood biomarker levels changes before and after PEMF treatment. Blood collected in normal red serum tubes will be used to assess anticancer potency in human breast cancer cells in vitro.

Activity and Diet Questionnaire

Study participants will be answering a set of questions on the day of blood collection (Week 1, 5 and 8) to help us gain insights about the changes to their daily routine activities or dietary intake which may contribute to the changes in the blood biomarkers levels.

6.1. Randomisation and Blinding

Prospective study participant will be given a subject ID (patient initials) by the clinical trial coordinator and a pre-screening questionnaire will be conducted to confirm the suitability. Personal data such as NRIC, date of birth are not collected using the questionnaire. A subject randomization ID (based on available RFID card number) will be assigned in addition to their subject ID. On the day of treatment, based on the subject randomization ID, the correct RFID card will be used to activate the PEMF leg coil. However, both parties will be blinded by the PEMF treatment administered to the upper thigh when the machine is switch on.

6.2. Study Visits and Procedures

[figure not shown]

Figure 3: Summary of study visits and procedures

a. Screening Visits and Procedures (Prescreening Visit)

Clinical trial coordinator will perform the recruitment screening. Eligible participants will be recruited and progress to Visit 1.

After participant has given the consent, assign the Subject Randomization ID which can be found on the RFID card.

b. Study Visits and Procedures (Visit 1-10)

Visit 1:

- Activity and diet questionnaire to be completed by the participant
- Blood will be collected from the participant into 2 EDTA tube and 1 red cap tube
- Verify the Subject ID and Randomization ID again before proceeding to use the assigned RFID card to activate the PEMF leg coil

Visit 2-8:

- Verify the Subject ID and Randomization ID again before proceed to use the assigned RFID card to activate the PEMF leg coil

Visit 9:

- Activity and diet questionnaire to be completed by the participant
- Blood will be collected from the participant into 2 EDTA tube and 1 red cap tube (one week after completion of Visit 1-8)

c. Final Study Visit (Visit 10):

Visit 11:

- Activity and diet questionnaire to be completed by the participant
- Blood will be collected from the participant into 2 EDTA tube and 1 red cap tube (four weeks after completion of Visit 1-8)

d. Post Study Follow up and Procedures

Should subjects experience any unlikely discomfort or irritation after treatment, they are free to report it to the study team.

e. Discontinuation Visit and Procedures

Should subjects experience any unlikely discomfort or irritation during treatment or blood collection procedure, they are free to report it to the study team and may ask to stop the treatment. Should subjects are already into the trial for 4 consecutive PEMF therapy (2 weeks, 4 visits), and if withdrawal occurs, subjects are required to return for a final study visit the following week for a final blood withdrawal. No other obligations required.

Subjects may withdraw voluntarily from participation in the study at any time.

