3.5. Withdrawal Criteria

Study participants will be withdrawn if unexpected adverse events arise through the course of the study. Participants who have missed more than 2 PEMF sessions will be withdrawn.

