9.4. Safety Monitoring Plan

The study team shall review study data quarterly. Adverse events and serious adverse events will be monitored for safety.

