k. Caffeine (e.g., caffeine tablets, daily coffee/tea)	Yes 	No 

4. Physical Activity

a. On average, how many steps do you take daily?	0 – 4999  5000 – 9999  10,000 – 14,999  Above 15,000 
b. Do you engage in more than 150 minutes of “moderate physical activity” a week? Yes  No 	Moderate physical activity noticeably increases your heart rate and breathing but still allow you to carry on a conversation. These activities are more intense than light activities. E.g., Brisk walking, cycling, dancing, hiking, tennis (doubles), recreational sports.
c. Do you also engage in more than 75 minutes of “vigorous-intensity physical activity” a week? Yes  No 	Vigorous-intensity activity will leave you saying no more than a few words without pausing for a breath. E.g., Race walking, running, swimming laps, badminton singles.
If  yes to (B) and/or (C), please indicate the activities below: e.g. Activity: Brisk walking, running, cycling, swimming, dancing, hiking, tennis, recreational sports etc. Frequency: (e.g. times per week); Duration: (minutes per session)	

Activity:	Frequency:	Duration:
Activity:	Frequency:	Duration:
Activity:	Frequency:	Duration:

d. How many sitting hours per day?

Visit 1 – Screening

Based on screening questionnaire, subject is included into study: Yes , No

(page 2 for screening assessment)

Remarks:

Completed by:

Name of Coordinator:

Signature:

Date:

Signature: Subject ID: -

Week 1 Visit 1

Date of Therapy: / / ; Day of therapy: _____ ; Time of therapy: :

Leg assignment: Left Right ; Name of Coordinator:

Week 1 Visit 2

Date of Therapy: / / ; Day of therapy: _____ ; Time of therapy: :

Leg assignment: Left Right ; Name of Coordinator:

Week 2 Visit 1

Date of Therapy: / / ; Day of therapy: _____ ; Time of therapy: :

Leg assignment: Left Right ; Name of Coordinator:

Week 2 Visit 2

Date of Therapy: / / ; Day of therapy: _____ ; Time of therapy: :

Leg assignment: Left Right ; Name of Coordinator:

Week 3 Visit 1

Date of Therapy: / / ; Day of therapy: _____ ; Time of therapy: :

Leg assignment: Left Right ; Name of Coordinator:

Week 3 Visit 2

Date of Therapy: / / ; Day of therapy: _____ ; Time of therapy: :

Leg assignment: Left Right ; Name of Coordinator:

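### Adverse events are to be monitored and can trigger withdrawal, but no visible visit procedure or form page asks about them or gives a place to record them after screening

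*Protocol*

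**What the plan says.** Two parts of the protocol depend on adverse-event data. Section 9.4 states: "The study team shall review study data quarterly. Adverse events and serious adverse events will be monitored for safety". Section 3.5 states: "Study participants will be withdrawn if unexpected adverse events arise through the course of the study". Section 9.1 defines an adverse event broadly, as any untoward medical occurrence, whether or not it is related to treatment.

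The capture route is in 6.2. After treatment (6.2(d)): "Should subjects experience any unlikely discomfort or irritation after treatment, they are free to report it to the study team". During treatment or blood collection (6.2(e)), participants with discomfort or irritation are told that "they are free to report it to the study team and may ask to stop the treatment".

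The visit procedures do not add an enquiry. For Visits 2 to 8 the whole listed procedure is: "Verify the Subject ID and Randomization ID again before proceed to use the assigned RFID card to activate the PEMF leg coil". Visit 9 and the final visit list the questionnaire and blood sampling. The schedule in Section 4 has columns for blood, the two treatment legs and the questionnaire. Section 6 gives the questionnaire's purpose as to "help us gain insights about the changes to their daily routine activities or dietary intake".

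In the Data Collection Form, each session has the date, day and time of therapy, and then "Leg assignment: Left Right ; Name of Coordinator". The Week 5 and Week 8 pages ask about long-term medication, supplements and physical activity. The only remarks line belongs to the screening decision.

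**The concern.** The protocol commits to acting on adverse events but fixes a method that waits for participants to mention them, and to mention only discomfort or irritation. A headache, a fall, a short infection or a disturbed night would be an adverse event under 9.1. A participant would have no prompt to raise it, and the coordinator would have no field for it.

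At stake is the safety statement that a pilot of this size is likely to make, namely that few or no events were seen. The value of that statement depends on whether anyone asked. The adverse-event withdrawal trigger in 3.5 and the review in 9.4 can act only on events that reach the team.

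**Working it through.** **Step 1: is there an adverse-event enquiry or field anywhere after screening?** The protocol states no event rate or safety sample size to reproduce, so the first check is textual.

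| Place in the protocol | What it records or asks | Adverse-event item? |
|---|---|---|
| Section 4, schedule | Blood, leg 1, leg 2, questionnaire | No |
| 6.2, Visit 1 | Questionnaire, blood, ID check, activation | No |
| 6.2, Visits 2 to 8 | ID check, activation | No |
| 6.2, Visit 9 and final visit | Questionnaire, blood | No |
| Form, eight session entries | Date, day, time, leg, coordinator | No |
| Form, Weeks 5 and 8 | Long-term medication, supplements, activity | No |
| 9.2 and 9.3 | Definitions and reporting clocks that start at first knowledge | No method of finding events |
| List of attachments | References, consent form, data collection form | No event log named |

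**Step 2: is there an indirect route through medication?** Section 8.3 says that all prescription and over-the-counter medication is recorded in the questionnaire at Weeks 1, 5 and 8. The form asks only whether the participant is on long-term medication. A short course taken for an event would not appear, so the form does not deliver what 8.3 states.

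**Step 3: what would zero reported events show?**

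Inputs:
- n = 18 active participants. This is an assumption: 36 participants (3.1) split equally. The protocol gives no allocation ratio.
- s = the share of affected participants who report unprompted. This is an assumption: 70%, 50% or 30%. The protocol gives no figure.

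With full capture, the one-sided 95% upper limit on the true risk p after 0 of 18 solves (1 − p)^18 = 0.05:

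p = 1 − 0.05^(1/18) = 0.153, or 15.3%.

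If each affected participant reports with probability s, the risk of a report is p × s. The limit therefore applies to p × s, and the limit on p is 0.153/s (computed from the unrounded value):

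| Share who report | Upper limit on true risk after 0 of 18 |
|---|---|
| 100% | 15.3% |
| 70% | 21.9% |
| 50% | 30.7% |
| 30% | 51.1% |

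**Step 4: the same point from the other side.** The chance of seeing at least one affected participant among 18 is 1 − (1 − p × s)^18. The true risks are assumptions.

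| True risk | s = 100% | s = 75% | s = 50% | s = 25% |
|---|---|---|---|---|
| 5% | 60% | 50% | 37% | 20% |
| 10% | 85% | 75% | 60% | 37% |
| 20% | 98% | 95% | 85% | 60% |

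At a true risk of 10%, halving the capture lowers the chance of seeing anything in the arm from 85% to 60%.

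**The case against.** **The gap may be filled out of sight.** Figure 3, which summarises visits and procedures, and the consent form could not be read, and either might carry adverse-event instructions. That caveat stands. No visible text, schedule column or listed attachment points to an event log, however, and the form, which is visible, has no field.

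**The study is a small, low-risk pilot with biomarker objectives.** This is true, and it keeps the point modest. The protocol nevertheless sets adverse-event monitoring and an adverse-event withdrawal trigger itself, so it needs a way to learn of events. This is a matter for the protocol and its form. An analysis plan cannot recover events that nobody asked about.

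**There are other routes.** Section 8.3 requires drugs or supplements prescribed during the intervention to be reported to the team. This is an indirect route and a partial answer. It misses untreated events, and for self-treated ones the form's item is too narrow.

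Four stronger readings are tempting, but the documents do not support them.

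- *A reader might infer that the trial collects no adverse-event data.* Volunteered reports do reach the team under 6.2(d) and (e). What is missing is systematic elicitation and a place to record.
- *A reader might infer that withdrawal in general is undermined.* Section 3.5 also withdraws participants who miss more than 2 sessions. That rule rests on session dates, which the form records. Only the adverse-event trigger is affected.
- *A reader might infer that quarterly review is too slow for a 4-week course.* Expedited reporting does not wait for it: 24 hours or 7 days under 9.2, and 7 or 15 days under 9.3. A participant may also ask to stop at any time. These clocks start at first knowledge, so they do not cure passive capture, but they do answer the timing complaint. Reviewing as each group of 10 finishes Week 4 would still come after all its sessions. It would also need 4 reviews (36/10, rounded up), the same as quarterly over the stated year (12/3 = 4).
- *A reader might infer a biased comparison of active with sham.* The protocol specifies no such safety comparison. Sections 6.1, 8.2 and 10.2 provide for blinding, so under-reporting should be similar in both arms.

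**Conclusion.** The point holds. The protocol relies on adverse events in 9.4 and in one of the two rules in 3.5. Its stated method of learning of them is participant-initiated report of discomfort or irritation, which is narrower than its own definition. No readable visit list, schedule or form page asks about events or records them after screening.

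The consequence is lost sensitivity. With complete reporting, a clean record in 18 participants would still leave risks up to 15.3% open. With 70% to 30% reporting it would leave open risks up to 21.9% to 51.1%. The 18 and the reporting shares are assumptions. The direction does not depend on them, but the size does, and the 51.1% is simply the 15.3% divided by 0.3. The textual finding is subject to what Figure 3 and the consent form contain.

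This should be put right before recruitment proceeds further, as a cheap improvement to the form. It is not a flaw in the trial's main design.

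**What to change.** Add one open question to the form at each session from Visit 2, and at the Week 5 and Week 8 visits: any new symptom or health problem since the last visit? For each positive answer, record onset, severity, seriousness, relatedness and outcome. List the enquiry in the 6.2 visit procedures and in the Section 4 schedule so that text and form agree. Widen the Week 5 and Week 8 medication item to cover all medication since the last assessment, as 8.3 already states.

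Leave the review interval in 9.4 and the missed-sessions rule as they are. The content of the adverse-event withdrawal rule is for the investigators; the form need only supply the information it depends on.

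The cost is one form page and about a minute at visits where a coordinator is already present. There are 7 sessions (Visits 2 to 8) plus 2 assessments, so 9 enquiries and about 9 minutes per participant. For 36 participants that is 36 × 9 = 324 minutes, or about 5.4 hours in all. The downside is that more minor events will be recorded and must be assessed.

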7. TRIAL MATERIALS

7.1. Trial Product: PEMF Leg Coil

The PEMF leg coil is a machine that produces low frequency electromagnetic fields in a defined area within a given amount of time. It uses electrical energy to direct a series of magnetic pulses through the skin and each magnetic pulse induces a tiny electrical signal in the cells and tissues. The machine consists of cylindrical PEMF coil apparatus, and a controller. The coils are enclosed in a polycarbonate case that completely isolates them from the user. All electronics are not assessable without complete disassembly of the apparatus with specialised tools. Any technical malfunction of the control unit or coil setup will result in a leakage current which triggers the earth leakage circuit breaker, protecting the user. The exposure time can be controlled by the user. The amplitude of magnetic fields used in this device is set at 1.5mT.

8. TREATMENT

8.1. Rationale for Selection of Dose

PEMF doses was recommended based on another study that was previously published where there were beneficial effects on participants who had received PEMF for 8-12 weeks. In this study, and to match the trial on oncology patients, subjects will be exposed to PEMF twice a week for 4 weeks.

8.2. Blinding

Double blinding will be performed using the RFID cards assigned to the study participants. The treatment details will be stored away by QuantumTX.

8.3. Concomitant therapy

All medications (prescription and over the counter), vitamin and mineral supplements, and / or herbs taken by the participant will be recorded in the questionnaire on Week 1, 5 and 8. Subjects requiring chronic dosing of any clinical drugs/prescriptive nutritional supplementations are excluded from the study. If subjects were given prescriptive drugs/supplements during trial intervention, they must be reported to the trial study team.

9. SAFETY MEASUREMENTS

9.1. Definitions

An adverse event (AE) is any untoward medical occurrence in subject administered a pharmaceutical product and which does not necessarily have a causal relationship with this treatment.

A serious adverse event (SAE) or reaction is defined as any untoward medical occurrence that at any dose:

1. Results in death
2. Is life-threatening
3. Requires inpatient hospitalization or causes prolongation of existing hospitalization
4. Results in persistent or significant disability/incapacity
5. May have caused a congenital anomaly/birth defect
6. Is a medical event that may jeopardize the patient and may require medical or surgical intervention to prevent one of the outcomes listed above.

9.2. Collecting, Recording and Reporting of “Unanticipated Problems Involving Risk to Subjects or Others” – UPIRTSO events to the NHG Domain Specific Review Boards (DSRB)

UPIRTSO events refers to problems, in general, to include any incident, experience, or outcome (including adverse events) that meets ALL of the following criteria:

1. Unexpected

In terms of nature, severity or frequency of the problem as described in the study documentation (eg: Protocol, Consent documents etc).

2. Related or possibly related to participation in the research

Possibly related means there is a reasonable possibility that the problem may have been caused by the procedures involved in the research; and

3. Risk of harm

Suggests that the research places participants or others at a greater risk of harm (including physical, psychological, economic, or social harm) than was previously known or recognized.

Reporting Timeline for UPIRTSO Events to the NHG DSRB.

1. Urgent Reporting: All problems involving local deaths, whether related or not, should be reported immediately – within 24 hours after first knowledge by the NHG investigator.
2. Expedited Reporting: All other problems must be reported as soon as possible but not later than 7 calendar days after first knowledge by the NHG investigator.

9.3. Collecting, Recording and Reporting of Serious Adverse Events (SAEs) to the Health Science Authority (HSA)

1. For Industry sponsored Trials

All SAEs will be reported to HSA according to the HSA Guidance for Industry “Safety Reporting Requirements for Clinical Drug Trials.”

2. For Principal Investigator initiated Trials

All SAEs that are unexpected and related to the study drug must be reported to HSA.

“A serious adverse event or serious adverse drug reaction is any untoward medical occurrence at any dose that:

- Results in death.
- Is life-threatening (immediate risk of death).
- Requires inpatient hospitalization or prolongation of existing hospitalization.
- Results in persistent or significant disability/incapacity.
- Results in congenital anomaly/birth defect.
- Is a Medically important event.

Medical and scientific judgment should be exercised in determining whether an event is an important medical event. An important medical event may not be immediately life threatening and/or result in death or hospitalization. However, if it is determined that the event may jeopardize the subject and/or may require intervention to prevent one of the other adverse event outcomes, the important medical event should be reported as serious.”

All SAEs that are unexpected and related to the study drug will be reported. The investigator is responsible for informing HSA no later than 15 calendar days after first knowledge that the case qualifies for expedited reporting. Follow-information will be actively sought and submitted as it becomes available. For fatal or life-threatening cases, HSA will be notified as soon as possible but no later than 7 calendar days after first knowledge that a case qualifies, followed by a complete report within 8 additional calendar days.

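### The adverse-event definition (9.1) and the investigator-initiated HSA trigger (9.3) name a drug, but the trial gives only a device or sham

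*Protocol*

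**What the plan says.** Section 9.1 of the protocol defines an AE as "any untoward medical occurrence in subject administered a pharmaceutical product" and adds that the event need not be caused by the treatment. The SAE definition that follows is worded differently: it is "defined as any untoward medical occurrence that at any dose" leads to one of six listed outcomes, with no mention of a pharmaceutical product.

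Section 9.3 gives two HSA branches. For industry-sponsored trials, "All SAEs will be reported to HSA according to the HSA Guidance for Industry", and the guidance cited is titled for clinical drug trials. For investigator-initiated trials, "All SAEs that are unexpected and related to the study drug must be reported to HSA". The closing text of 9.3 repeats the second rule as the commitment for this study: "All SAEs that are unexpected and related to the study drug will be reported". The deadlines attach to that sentence: 15 calendar days in general, and 7 calendar days for fatal or life-threatening cases with a complete report within 8 more.

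On the product, section 7.1 says: "The PEMF leg coil is a machine that produces low frequency electromagnetic fields". On the arms, section 5.1 says: "Participant will receive either PEMF or no PEMF twice in a week for 4 consecutive weeks".

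**The concern.** An AE definition and a regulatory reporting trigger are operative rules that staff apply event by event, and they belong in the protocol itself. Here both point to a product that neither arm is given. Taken at their word, skin irritation under the coil or a problem at blood collection is not an AE by virtue of taking part in the trial, and an SAE caused by the coil does not meet the investigator-initiated HSA condition.

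Other rules depend on the AE term. Section 3.5 withdraws participants for unexpected AEs, section 3.6 replaces those withdrawn, and section 9.4 has the study team monitor AEs and SAEs in a quarterly data review. A definition with the wrong object therefore reaches beyond the safety listing, into who stays in the trial.

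**Working it through.** No calculation applies, because the point depends on no sample size, error rate or effect. The check sets the clauses of section 9 against the product and the arms.

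**Step 1: what is given.** Sections 5.1 and 7.1 describe a device, delivered or not delivered. No study drug appears in either arm, and no section says that the drug terms in section 9 are to be read as the coil.

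**Step 2: each safety clause against that product.**

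| Clause | Condition on the product | Works for this trial as written? |
|---|---|---|
| AE definition, 9.1 | Pharmaceutical product administered | No |
| SAE definition, 9.1 | None; refers to any dose, and 1.2 and 8.1 speak of PEMF doses | Yes |
| HSA, investigator-initiated, 9.3 | Unexpected and related to the study drug | No |
| HSA, closing text of 9.3 with the 7/15-day clocks | Same | No |
| HSA, industry-sponsored, 9.3 | None on relatedness; all SAEs | Yes, but the cited guidance is titled for drug trials |
| UPIRTSO to the ethics board, 9.2 | Related or possibly related to taking part in the research | Yes |

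For UPIRTSO, a possible relation is a reasonable possibility that the problem "may have been caused by the procedures involved in the research". That wording takes in both the coil and blood collection. Local deaths go to the ethics board within 24 hours whether related or not.

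**Step 3: which HSA branch applies.** The text does not say outright. The closing text of 9.3 uses the investigator-initiated wording and makes the investigator responsible for informing HSA, but both branches are left standing.

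**Step 4: does reading PEMF for drug repair it?** Only in part.
- The AE definition would then cover participants given PEMF. Sham participants receive none and would stay outside it.
- Under section 10.2 the principal investigators and participants stay blinded until study completion, so they could not tell whom the definition covers.
- Week 1 blood is taken before the first PEMF session (section 6), so an event at that draw precedes any exposure in either arm.
- An SAE caused by blood collection would be related to a procedure and not to PEMF, so it would still miss the HSA trigger in both arms.

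**The case against.** The best reply is that this is leftover drug-template wording that nobody would misapply. The AE sentence itself goes on to speak of the treatment, section 8 uses that word for PEMF, and there is no drug with which to confuse the coil. Staff would probably read the device into the text. That stands as a comment on likely practice, and it is why the point is a wording defect and not a failure of the safety system. It does not remove the point, because the natural substitution still leaves out sham participants and blood-collection events (Step 4).

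Stronger readings are tempting, but the documents do not support them:
- *That safety reporting is disabled, or that UPIRTSO is the only route left.* The SAE definition and the industry-sponsored branch carry no drug condition. Section 9.4 monitors SAEs, and section 6.2 leaves participants free to report discomfort or irritation to the study team.
- *That UPIRTSO misses events not clearly related to the device.* Its relatedness criterion is met by a possible relation. It does leave out expected events, but that is the purpose of a route for unanticipated problems.
- *That a count of participants outside the definition measures the defect.* Such a count only restates the literal reading. Section 8.3 also expects some participants to take medicines, and they could meet the words of the AE definition incidentally.
- *That the arms could not be compared on safety.* The literal wording treats both arms alike, and the objectives in 2.2 and 2.3 set out no between-arm safety comparison. Such a loss is speculation.

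**Conclusion.** The point holds in a limited form. The AE definition in 9.1 and the investigator-initiated HSA trigger in 9.3, with its restatement, are wrong as written for a device trial. They do not capture events in PEMF or sham participants through the trial intervention, and they do not start the 7- and 15-day HSA clocks. Three sentences are affected (one definition, and one trigger stated twice), plus one guidance reference that does not match the product.

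The conclusion assumes that the terms carry their ordinary meaning, since the protocol gives no other. The HSA part also assumes that the investigator-initiated branch applies, as the closing text of 9.3 suggests without saying so. If the industry-sponsored branch applies, all SAEs are reportable, and what remains is the AE definition, the conflicting closing text of 9.3 and the drug-trial guidance reference. The biomarker objectives are not affected. The text should be corrected, and nothing in the design needs to change.

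**What to change.** Amend section 9 as follows.
- **9.1:** define an AE as any untoward medical occurrence in a participant assigned to active or sham PEMF, whether or not it is considered related to the device or to a study procedure, including blood collection.
- **9.3, including its closing text:** replace the study-drug wording with study device or study procedure.
- **9.3:** state which HSA branch applies to this trial, and reconcile the drug-trial guidance reference with the device in 7.1. The protocol does not settle which HSA route governs a device study, so the sponsor must confirm and name it.

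The cost is a wording amendment to one section, with no additional visits, staff or participants.
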